RRH	Rapid Rehousing Assistance
VI-SPDAT	Vulnerability Index – Service Prioritization Decision Assistance Tool

PROTOCOL SYNOPSIS

TITLE	Silicon Valley Guaranteed Income Pilot
SPONSOR	
FUNDING ORGANIZATION	UCSF Benioff Homelessness and Housing Initiative
NUMBER OF SITES	1
RATIONALE	
Homelessness is a national public health crisis in the United States. Over 600,000 people experience homelessness on any given night, with Black, Indigenous, and People of Color (BIPOC) disproportionately affected, and with the highest rates of homelessness in regions with high housing costs. Individuals experiencing homelessness have high rates of chronic physical and mental health conditions, are at higher risk for contracting, transmitting, and suffering complications from communicable illnesses, and more frequently need emergency and acute health services. The cumulative consequences of homelessness are massive human suffering and strain on essential public health and medical systems, which spend vast resources on treating the downstream health sequelae of chronic homelessness. Guaranteed income (i.e., unconditional cash transfer) is a promising intervention for reducing poverty and material hardship but there are few U.S.-based studies on guaranteed income overall, and none designed for alleviating homelessness. Thus, our objective is to assess the effect of guaranteed income on housing stability among individuals experiencing homelessness.

STUDY DESIGN	Randomized controlled trial
PRIMARY OBJECTIVE	Assess the effect of guaranteed income on receipt of stable housing
SECONDARY OBJECTIVES	Assess the effect of guaranteed income on the health and well-being of families experiencing homelessness
NUMBER OF PARTICIPANTS	300
PARTICIPANT SELECTION CRITERIA	
Inclusion Criteria: Families with children experiencing homelessness in Santa Clara County
 
Exclusion Criteria: Substantial/severe level of problematic substance use; Hazardous/harmful alcohol consumption and/or active and severe alcohol use disorder

TEST PRODUCT, DOSE, AND ROUTE OF ADMINISTRATION	A total of \$24,000 will be disbursed to participants in the intervention group over a period of 24 months.
CONTROL PRODUCT, DOSE AND ROUTE OF ADMINISTRATION	Usual care
DURATION OF PARTICIPANT PARTICIPATION AND DURATION OF STUDY	
Participants will be followed for 36 months after enrollment.
 
Follow-up: 36 months (24 concomitant with period over which participants will be receiving guaranteed income, plus an additional 12 months after the end of guaranteed income payments).
 
The total duration of the study is expected to be 48 months. 12 months for participant recruitment and 36 months for final participant follow-up.

CONCOMMITANT INTERVENTIONS	Allowed: Any and all other federal, state, county, and local/community assistance services that are available to participants
EFFICACY EVALUATIONS	
PRIMARY ENDPOINT	Our primary endpoint is number of days experiencing homelessness
SECONDARY ENDPOINTS	
 • Time spent unsheltered and/or in unstable housing; physical, mental, social, financial well-being; use of health care and public assistance/social services
STATISTICS Primary Analysis Plan	We will conduct intention-to-treat analyses to assess our primary endpoint, including difference in numbers of days spent homeless using Poisson regression
Rationale for Number of Participants	Our community partner service organizations have resources to provide guaranteed income assistance to 150 families; we plan for a total of 300 participants to enable enrollment of a control group of equal size.

1 BACKGROUND

Homelessness is a national public health crisis in the United States. Over 600,000 people experience homelessness on any given night, with Black, Indigenous, and People of Color (BIPOC) disproportionately affected, and with the highest rates of homelessness in regions with high housing costs. Individuals experiencing homelessness have high rates of chronic physical and mental health conditions, are at higher risk for contracting, transmitting, and suffering complications from communicable illnesses, and more frequently need emergency and acute health services. The cumulative consequences of homelessness are massive human suffering and strain on essential public health and medical systems, which spend vast resources on treating the downstream health sequelae of chronic homelessness. Guaranteed income (i.e., unconditional cash transfer) is a promising intervention for reducing poverty and material hardship with a robust evidence base from studies conducted in developing countries. However, there are few U.S.-based studies on guaranteed income overall, and none published on the effectiveness of guaranteed income in alleviating homelessness.

1.1 Overview of Studies

Conceptually, guaranteed income is simple: give a meaningful sum of money directly to people so they are empowered to make purchasing and investment decisions for their own well-being. This is in contrast to existing financial assistance programs to alleviate homelessness which demonstrate promising results but have significant limitations as follows: a) consist of brief periods of assistance; b) are restricted to direct housing-related needs such as rental assistance or moving and utility costs; c) lack flexibility and do not account for the complex and potentially idiosyncratic needs of different families; and d) are associated with high per-person administrative costs.

Guaranteed income (i.e., unconditional cash transfer) is a promising intervention for reducing poverty and material hardship with a robust evidence base from studies conducted in low- and middle-income countries demonstrating decreased monetary poverty, decreased food insecurity, increased school attendance, increased savings, increased work participation, improved access to health care services, and improved child health. Despite the international evidence base, there are few published studies based in the U.S. or in other high-income countries on guaranteed income overall and none published on the effectiveness of guaranteed income in alleviating homelessness, though a number of pilot studies in a variety of settings and populations within the U.S. are currently pending. One study based in Vancouver, Canada assessed the impact of a single lump sum payment equivalent to \$5,700 USD on time to housing; preliminary findings suggest that this form of cash assistance helped reduce time to stable housing and improved food security. A second study, the Denver Basic Income Project, will assess the impact of varying unconditional cash transfer payment strategies (monthly vs lump sum vs hybrid) on homelessness over a one-year period of payments; the study will start in Spring 2022.

2 STUDY RATIONALE

Although guaranteed income is a promising intervention for reducing poverty and material hardship, there are few U.S.-based studies on guaranteed income overall, and none published on the effectiveness of guaranteed income in alleviating homelessness. This study will be among the first studies of guaranteed income among families experiencing homelessness in the U.S. and will assess the impacts of guaranteed income over a longer duration (two years) than any other study targeted at individuals experiencing homelessness (other known studies have assessed or are planning to assess outcomes only up to one year).

2.1 Risk / Benefit Assessment

The main risks of receiving guaranteed income (GI) are the same as the risks that would be incurred by the general population in daily life who experience any increase in overall household income: 1) increased income tax burden; and 2) the potential loss of existing public benefits and assistance among participants. Our community partners have primary responsibility for administering and implementing the guaranteed income intervention, and have developed a comprehensive approach to mitigating these risks, including a) limiting the total annual amount of GI to \$12,000 per year, an amount that is considered a non-taxable gift rather than income by the Internal Revenue Service and therefore would not be subject to income tax; b) negotiating waivers to ensure that GI is exempt from being included in eligibility calculations for Santa Clara County and California state assistance services such that participants will maintain the same eligibility for services they would have in the absence of GI; c) providing individualized benefits counseling during the study enrollment process so that potential participants can make informed decisions about participation prior to enrolling in the study; and d) creating a Hold Harmless fund to reimburse participants for any unanticipated benefits losses. The primary potential benefit of guaranteed income is that it will act to enhance and supplement existing housing and social assistance services and decrease homelessness and improve housing stability, health, and well-being of participants. These potential benefits outweigh the risks to participants.

The main risks of participating in our research evaluation activities are loss of privacy and confidentiality. There is also the risk of disappointment at not being selected for the guaranteed income intervention group. Our research evaluation activities involve secondary analyses of administrative program data, and prospective data collection through administration of surveys and conducting structured and semi-structured interviews. Our research study team will put into place comprehensive measures to protect the privacy of participants and confidentiality of their data, including a) conducting eligibility screening, informed consent, surveys and interviews by trained research staff in-person and/or by telephone in private settings where responses will not be overheard; b) informing and emphasizing that we will not disclose individual and/or identifiable data collected for the study to anyone outside of the immediate research study team including community partners, community service providers, and/or community members; c) ensuring that identifying information about individual participants will never be included in manuscripts or other presentations of data; d) storing all electronic research data on a secure, encrypted database on a UCSF server that is backed up nightly; e) storing all hard

copies of data in locked, secured cabinets behind locked office doors; and f) de-identifying data for analysis by coding data for a unique evaluation identification number for each participant, and storing the document linking participant identifiers to evaluation identification numbers separate from research data and destroying this document at the end of the evaluation. There will no immediate benefit to participants participating in research evaluation activities, though consent and enrollment in the research evaluation will be a prerequisite to being eligible to being randomized to receive the guaranteed income intervention. Individuals who are randomized to the guaranteed income intervention group will benefit from receiving the income payments.

3 STUDY OBJECTIVES

3.1 Primary Objective

The primary objective of this study is to assess the effect of guaranteed income on housing stability.

3.2 Secondary Objectives

The secondary objectives of this study are to assess the effect of guaranteed income on the health and well-being of families with children experiencing homelessness.

4 STUDY DESIGN

4.1 Study Overview

This is a single-site, single-blinded randomized controlled trial. The community partner service organizations, Destination: Home SV and the ¡Sí Se Puede! Collective, have raised funds to provide unconditional cash assistance in the form of guaranteed income (GI) for a period of two years to 150 families with children experiencing homelessness in Santa Clara County and who are eligible for referral to rapid rehousing assistance programs (RRH). The partner service organizations are prioritizing assistance to those awaiting RRH referral given the current extended wait time for RRH services. Because there are far more families who are eligible for GI than there are available resources, 150 eligible families will be randomly selected to receive GI. From the pool of eligible families, we will also randomly select an additional 150 participants as matched controls for the purpose of evaluation.

Thus, we are planning for a total of 300 participants. Participants will be assigned to either the control (usual care) or intervention (guaranteed income) groups in random order. Evaluations will be taken at baseline and every 6 months monthly via in-person and/or telephone assessments.

Screening data will be reviewed to determine participant eligibility. Participants who meet all inclusion criteria and none of the exclusion criteria will be entered into the study.

The following treatment regimens will be used:

- Intervention – guaranteed income, consisting of a total of \$24,000 to be disbursed over 24 months. Participants may opt for either monthly (\$1,000/month) or hybrid (lump sum of \$6,500 the first month, then \$500/month x 11 months for a total of \$12,000 per

year) disbursement schedules, with the option to switch disbursement schedule after the first 12 months. Participants will also be invited to attend a Public Benefits Information Session to learn about public benefits and social assistance programs available to residents of Santa Clara County. Participation in this Benefits Information Session will be optional and not required for study participation.

- Control – usual care as per the partner service organizations. Participants will be invited to also attend a Public Benefits Information Session to learn about public benefits and social assistance programs available to residents of Santa Clara County. Participation in this Benefits Information Session will be optional and not required for study participation.

Total duration of participant participation will be 36 months from the time of enrollment. Total duration of the study is expected to be 48 months (12 months for recruitment and 36 months for follow-up from the time of last participant enrolled).

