11 ADVERSE EXPERIENCE REPORTING AND DOCUMENTATION

11.1 Adverse Events

The study team will probe, via discussion with the participant, for the occurrence of adverse events (AEs) during each participant visit and record the information in the site's

source documents. Adverse events will be recorded in the patient CRF. Adverse events will be described by duration (start and stop dates and times), severity, outcome, treatment and relation to study intervention, or if unrelated, the cause. For this study, the primary potential adverse events of concern associated with the study intervention are potential loss of existing public benefits and assistance among participants, and increased income tax burden, similar to the risks that would be incurred by the general population in daily life who might experience a similar increase in overall household income.

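### The $12,000-a-year limit behind the income-tax assurance is kept per payment year; a permitted monthly-to-hybrid switch can put up to $17,500 into one calendar year

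*Protocol*

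**What the plan says.** Protocol section 2.1 (Risk / Benefit Assessment) names two main risks of the payments: a higher income tax burden and loss of public benefits. Its first mitigation is "limiting the total annual amount of GI to \$12,000 per year", described as "an amount that is considered a non-taxable gift rather than income by the Internal Revenue Service". From this the section concludes that no income tax would arise. The other listed mitigations are waivers on benefit eligibility, benefits counselling at enrolment, and a Hold Harmless fund for lost benefits.

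Section 4.1 (Study Overview) sets a total of $24,000 "to be disbursed over 24 months". It says "Participants may opt for either monthly (\$1,000/month) or hybrid", with hybrid defined as a "lump sum of \$6,500 the first month, then \$500/month x 11 months", and it labels the resulting $12,000 a yearly total. Families choose a schedule "with the option to switch disbursement schedule after the first 12 months". The direction of the switch is not restricted, and payments are not tied to a calendar or tax year. The same section plans "12 months for recruitment and 36 months for follow-up from the time of last participant enrolled".

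Section 11.1 (Adverse Events) lists loss of benefits "and increased income tax burden, similar to the risks that would be incurred by the general population" as the adverse events of main concern.

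**The concern.** The limit has one stated purpose, which is tax treatment. A limit that serves a tax purpose has to hold over the period in which tax is reckoned. Section 4.1 holds it over a different period: 12 payments starting whenever a given family happens to start. With recruitment spread over 12 months, those starts can fall in different calendar months.

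The two periods give the same answer as long as a family keeps one schedule. They diverge when a family on level monthly payments switches to the front-loaded schedule, because the tail of the $1,000 payments and the $6,500 lump sum can then land in the same calendar year.

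What is at stake is the accuracy of a risk statement made about families experiencing homelessness. Increased tax burden is one of only two adverse events that section 11.1 singles out. Of the mitigations in section 2.1, only the annual limit addresses it. The one counselling step that section 2.1 describes is at enrolment, about a year before the switch is chosen, and concerns benefits.

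**Working it through.** **Inputs.** Annual limit $12,000 (section 2.1). Monthly schedule $1,000 per month; hybrid schedule $6,500 in the first month, then 11 payments of $500; total $24,000; switch allowed after month 12; recruitment over 12 months (all section 4.1).

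**Assumptions.** The tax year is the calendar year. Payments are made once each calendar month without gaps. A switch takes effect at payment 13, and the new schedule is then followed in full. The documents state none of these outright, although a full second schedule is what brings the total to $24,000.

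**Step 1: reproduce the protocol's figures.**

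- Monthly: 12 × 1,000 = $12,000.
- Hybrid: 6,500 + 11 × 500 = 6,500 + 5,500 = $12,000.
- Any two-year sequence: 12,000 + 12,000 = $24,000.

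Counted by payment year, every permitted sequence meets the limit exactly.

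**Step 2: monthly then hybrid, by calendar year.** Let s be the calendar month of the first payment (January = 1). The first calendar year holds 13 − s payments. The second holds the remaining s − 1 monthly payments, the lump sum, and 12 − s payments of $500:

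1,000(s − 1) + 6,500 + 500(12 − s) = 11,500 + 500s.

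| First payment | Calendar year 1 | Calendar year 2 | Calendar year 3 | Total |
|---|---|---|---|---|
| January (s = 1) | $12,000 | $12,000 | $0 | $24,000 |
| February (s = 2) | $11,000 | $12,500 | $500 | $24,000 |
| July (s = 7) | $6,000 | $15,000 | $3,000 | $24,000 |
| December (s = 12) | $1,000 | $17,500 | $5,500 | $24,000 |

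The second-year total exceeds $12,000 for every s from 2 to 12, that is for 11 of 12 start months. The excess over the limit is 500(s − 1), from $500 to $5,500. For December the sum is 11 × 1,000 + 6,500 = $17,500.

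**Step 3: the other three sequences, second calendar year.**

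- Monthly throughout: 12 × 1,000 = $12,000.
- Hybrid throughout: 500(s − 1) + 6,500 + 500(12 − s) = $12,000.
- Hybrid then monthly: 500(s − 1) + 1,000(13 − s) = 12,500 − 500s, at most $12,000.

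Their first and third calendar years also stay at or below $12,000 for every start month. The excess is therefore confined to one permitted path.

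**Step 4: does this depend on a January tax year?** No. If a fixed 12-month tax year began in some other month, s would count months from that point and the same formula would apply. After this switch, only families whose first payment falls in the first month of the tax year stay at $12,000.

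**The case against.** The strongest reply is that sections 2.1 and 4.1 agree as written. Section 4.1 itself builds the annual $12,000 from 12 payment months, and on that count no permitted sequence exceeds it. This stands. A reader might infer that the switch option breaks the protocol's limit outright, but the documents do not support that: it follows only if the year is the tax year, which neither section says. The payment-year reading has its own difficulty, though. It keeps the number but not the reason given for it, because a limit counted from each family's first payment does not by itself support a statement about tax.

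A second reply is that no tax consequence has been shown. This also stands. A reader might conclude that the mitigation fails and that switching families will owe tax. Section 2.1 says that $12,000 is treated as a gift; it does not say that $12,500 or $17,500 would not be.

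A third tempting reading is that any family that switches receives $17,500 within 12 consecutive payments. That is true of payments 2 to 13 only for monthly-to-hybrid (11 × 1,000 + 6,500). For hybrid-to-monthly the same payments total 11 × 500 + 1,000 = $6,500. In any case, neither section applies the limit to a rolling window.

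It is also fair to say that the community partners run the payments and may time switches under rules not shown here, that the consent pages are not available, and that section 11.1 has staff ask about adverse events at each visit. Asking would help detect a tax problem after the fact; it would not make the section 2.1 statement accurate.

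**Conclusion.** The point holds as a mismatch between the purpose of the limit and the period over which the payment rule keeps it. Under the assumptions listed with the calculation, a family switching from monthly to hybrid receives between $12,000 and $17,500 in its second calendar year, above the limit for 11 of 12 start months. No other sequence exceeds $12,000.

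The documents do not settle whether any tax would be due, how many families would switch in this direction, or how payment starts are spread over the year, so the number of families affected cannot be estimated. Sample size, power and the primary analysis are untouched. The matter is the accuracy of a participant-risk statement. It should be corrected because the assurance as written goes further than the payment rule supports.

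**What to change.** Reconcile sections 2.1 and 4.1. First, state the year over which the $12,000 limit is counted: payment year, calendar year or tax year. Then do one of two things:

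- make the switch option in section 4.1 consistent with the limit so defined; or
- restate the section 2.1 assurance with the largest amount that a monthly-to-hybrid switch can place in one tax year ($17,500 under the calendar-year assumption), and have its tax treatment confirmed.

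If the switch option stays as it is, give families that figure before they make the month-12 choice, and bring any participant information that repeats the assurance into line. The sponsor and community partners should decide which section governs.

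The cost is a short protocol amendment and matching participant wording. Restating the assurance changes no total funds, sample size, assessments or analysis.

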5 CRITERIA FOR EVALUATION

5.1 Primary Efficacy Endpoint

Our primary endpoint is number of days experiencing homelessness (with ‘homelessness’ as defined below in section 6.2) during the study period.

For our primary endpoint, number of days experiencing homelessness, given our sample size of 300 with 150 participants in each arm, we estimate that we will have 80% power at a two-sided significance level of 0.05 to detect a mean reduction of 24.0 days in the intervention group, assuming a mean of 52.3 ± 74.0 days experiencing homelessness from prior studies. Allowing for a 27% dropout rate as estimated from prior studies (for a total of sample size of 220 participants with 110 families in each arm), we will still have 80% power at a two-sided significance level of 0.05 to detect a mean reduction of 28.0 days in the intervention group.

